## **11. DATA REPORTING / REGULATORY CONSIDERATIONS**

### **11.1 Data Collection**

The data collection plan for this study is to utilize REDCap to capture all treatment, toxicity, and efficacy data for all enrolled patients.

#### **11.1.1 REDCap**

[figure not shown]
REDCap (Research Electronic Data Capture) is a free data management software system that is fully supported by the Weill-Cornell Medical Center CTSC. It is a tool for the creation of customized, secure data management systems that include Web-based data-entry forms, reporting tools, and a full array of security features including user and group based privileges, authentication using institution LDAP system, with a full audit trail of data manipulation and export procedures. REDCap is maintained on CTSC-owned servers that are backed up nightly and support encrypted (SSL-based) connections. Nationally, the software is developed, enhanced and supported through a multi-institutional consortium led by the Vanderbilt University CTSA.

### **11.2 Regulatory Considerations**

All protocol amendments and consent form modifications will be made by the Principal Investigator.

## **12. STATISTICAL CONSIDERATIONS**

Data analysis and image interpretation will be performed in a manner similar to the strategy employed by Osborne et al. and Turkbey B et al, with both a lesion specific and sector-specific analysis. For the sector-analysis, the prostate gland will be divided into segments as described in the START criteria. A lesion-based analysis will also be performed after review of histopathology.

Sectors of the prostate gland as described by the START criteria, Moore C, et al.

## 12.1 Study Design/Endpoints

The present study is a phase II, open label, single-center, non-randomized, single-dose study.

### Primary endpoints

The primary endpoint of this study is the proportion of subjects with PSMA-positive (identified by H&E staining and immunohistochemistry) "dominant" PC lesion(s) greater than 5mm in diameter, whose lesion(s) have been successfully identified by  $^{89}\text{Zr}$ -df-IAB2M imaging. Because this is an exploratory pilot study, no formal sample size/power calculation is required. However, with a sample size of 20 patients in the study, a two-sided 95% confidence interval for the proportion of patients successfully imaged by  $^{89}\text{Zr}$ -df-IAB2M can be constructed to be within  $\pm 19.0\%$  of the observed proportion of patients with successful imaging by  $^{89}\text{Zr}$ -df-IAB2M. This calculation assumes an  $^{89}\text{Zr}$ -df-IAB2M imaging-success proportion of 75%. All estimates from the study will serve as preliminary data (i.e., hypothesis-generating) for future studies.

- Descriptive statistics will be calculated for the study cohort:
  - Median and inter-quartile range or mean and standard deviation for age, biopsy Gleason score (1o, 2o, Total), number of cores on biopsy, number of positive cores on biopsy, PSA, number of lesions on prostatectomy pathology (RP pathology), lesion size on RP pathology, Gleason score (1o, 2o, and total) on RP pathology.
- Lesion-based analysis:

- SUVmax measurements of Zr-df-IAB2M PET/CT images obtained in tumor and non-tumor regions will be compared. To account for inpatient correlation of multiple lesions, a linear mixed-effects model with a random intercept will be used to estimate and compare the mean SUVmax values in different regions.  $P < 0.05$  will be indicative of a significant difference as described by Turkbey B, et al.
- Positive and negative predictive values will be estimated by using generalized estimating equations (GEE) modeling, with logit link function and a working independence correlation structure. Robust variance estimation and the delta method will be used to calculate standard errors of the positive and negative predictive values. The Wald test with robust variance estimates will be used for statistical inference. Subgroup analyses will be performed for high, moderate, and low risk disease (see secondary endpoints).
- Receiver operating curve characteristics (ROC) will be constructed to determine the predictive ability of SUV level on detection of any disease and disease severity as correlated to histopathology.

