## 1. OBJECTIVES

### 1.1. Primary Objectives

- To evaluate the ability of  $^{89}\text{Zr}$ -df-IAB2M to detect localized, clinically significant (defined as:  $\geq 0.5 \text{ cm}^3$  with Gleason pattern  $\geq 4$ ) prostate cancer (PCa).

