#### 9.1.2 $^{89}\text{Zr}$ -df-IAB2M PET/CT imaging

##### 9.1.2.1 Method of Assessment

PET/CT will be read twice by a nuclear medicine physician. For the first interpretation, the physician will be blinded from clinical history, biopsy results and conventional

imaging modalities. After the initial reading, the nuclear medicine physician will be provided with both the TRUS biopsy results and previously read scans for the repeat PET/CT reading. During each interpretation, the physician will record all abnormal, suspicious areas with higher uptake than adjacent or contralateral background. Each abnormal area will be recorded on a map of the prostate along with maximum standardized uptake value ( $SUV_{max}$ ) and mean standardized uptake value ( $SUV_{mean}$ ).

Subsequently, the accumulation of  $^{89}Zr$ -df-IAB2M will be compared to areas of known PCa foci on histopathology and mpMRI, as described in Section 13. After completion of the histopathology, the PET/CT findings will be compared to histopathology to perform a lesion by lesion analysis with histopathology serving as the reference gold standard. This analysis will primarily include tumors  $\geq 0.5 \text{ cm}^3$  on histopathology, with a secondary assessment of any lesions  $<0.5 \text{ cm}^3$ . Similarly, areas of increased uptake identified on IAB2M, which had been read as suspicious for cancer will be compared to histopathology to determine the underlying pathology (e.g., inflammation, benign prostatic hyperplasia).

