### Secondary endpoints

- To determine the ability of *in vivo* Zr-df-IAb2M PET/CT to correlate with pathological features (i.e. Gleason pattern, diameter and PSMA-positivity):
  - The Wilcoxon rank sum test will be used to compare lesions that were and were not identified on *in vivo* PET with respect to lesion size, immunohistochemical PSMA staining, and Gleason score (demonstrated by histopathology). This lesion based analysis will be performed in a similar fashion as described above.
- To compare the *in vivo* Zr-df-IAb2M PET/CT and Ga-PSMA-HBED-CC PET/CT to *in vivo* mpMRI:
  - The diagnostic accuracy of Zr-df-IAB2M PET/CT and Ga-PSMA-HBED-CC PET/CT imaging in patients with prostate cancer will be compared with that of mpMRI imaging by using sector-based analysis, as described by Turkbey B et al. The estimates of patient-specific sensitivity and specificity will be defined as the proportion of true-positive sectors and the proportion of true-negative sectors in each patient. Overall sensitivity and specificity will then be estimated by calculating the mean (and standard error) of these individual-

specific estimates across patients. Differences in sensitivity and specificity between modalities will then be evaluated by the Wilcoxon signed-rank test.

- To determine the sensitivity, specificity, PPV, NPV of IAB2M to detect all pathologically identified PCa lesions that do not meet criteria for clinical significance (defined as:  $< 0.5 \text{ cm}^3$  with Gleason pattern  $< 4$ ):
  - As above, but for lesions considered not to be clinically significant.
- To correlate IAB2M positivity (SUV) and lesion size:
  - The Spearman-rank correlation coefficient will be used to evaluate the association between SUV and size of the lesion (procedure for size measurements are defined in Section 9.1.3).
- To correlate IAB2M positivity (SUV) and Gleason pattern (3, 4 and 5):
  - The Spearman-rank correlation coefficient will be used to evaluate the association between correlate SUV and the histopathologically defined Gleason pattern. The Wilcoxon rank-sum test will also be used to compare  $\text{SUV}_{\text{max}}$  measurements between lesions with low Gleason score (3+4 or lower) and high Gleason score (4+3 or higher).
- To correlate IAB2M positivity (SUV) and PSA:

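### The primary objective and the primary endpoint describe different lesions, and no stated analysis gives a detection proportion for the lesions the objective names

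*Combined protocol and SAP*

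**What the plan says.** Section 1.1 gives a single primary objective, to evaluate the ability of the tracer "to detect localized, clinically significant (defined as" a volume of at least 0.5 cm³ with Gleason pattern 4 or higher).

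Section 12.1, Primary endpoints, says: "The primary endpoint of this study is the proportion of subjects with PSMA-positive (identified by H&E staining and immunohistochemistry") and dominant "PC lesion(s) greater than 5mm in diameter, whose lesion(s) have been successfully identified by" the tracer's imaging. Dominance is not defined there or elsewhere.

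Three other places come close to the objective:
- Section 9.1.2.1 plans a lesion-by-lesion comparison with histopathology. "This analysis will primarily include tumors" of at least 0.5 cm³, with smaller lesions assessed secondarily. It sets no grade condition.
- Section 12.1, Secondary endpoints, defines sensitivity for the comparison with mpMRI by sector: "The estimates of patient-specific sensitivity and specificity will be defined as the proportion of true-positive sectors" and, for specificity, of true-negative sectors.
- The same section plans sensitivity, specificity, PPV and NPV for lesions that are not clinically significant. The whole method is: "As above, but for lesions considered not to be clinically significant".

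Sections 12.1 and 12.2 state a precision of ±19.0 points for 20 patients at an assumed success proportion of 75%. Section 12.3 adds an interim efficacy determination on the primary endpoint once the first 10 patients have had surgery and histopathology.

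**The concern.** The objective asks whether the tracer finds clinically significant cancer. The endpoint reports whether it finds PSMA-positive, dominant lesions above a much smaller size, at any grade. A reader of the final report would naturally take the primary result as the answer to the primary objective, and it would not be.

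Three uses of the result are affected: the interpretation of the main result, the interim efficacy determination after 10 patients, and the planning of later studies, for which Section 12.1 says the estimates are intended. Because the study calls itself an exploratory pilot, no confirmatory claim or error rate is at risk.

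**Working it through.** **1. The plan's own figure.** Inputs from Sections 12.1 and 12.2: n = 20, p = 0.75, two-sided 95%. The Wald half-width is 1.96 × √(p(1 − p)/n) = 1.96 × √(0.75 × 0.25/20) = 0.1898, or 19.0 points. The stated figure reproduces.

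**2. Size thresholds on one scale** (assuming spheres, V = πd³/6):
- d = 5 mm: π × 0.5³/6 = 0.065 cm³.
- d = 7 mm: π × 0.7³/6 = 0.180 cm³.
- V = 0.5 cm³: d = (6 × 0.5/π)^(1/3) = 0.985 cm = 9.85 mm.
- Ratio of volume thresholds: 0.5/0.0654 = 7.6.

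A diameter does not fix the volume class of an irregular lesion. An ellipsoid of 15 × 7.5 × 7.5 mm has volume π/6 × 1.5 × 0.75 × 0.75 = 0.44 cm³, below the objective's cut-off although it is 15 mm long.

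**3. The two definitions side by side.**

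| Attribute | Objective (1.1) | Endpoint (12.1) |
|---|---|---|
| Size | at least 0.5 cm³ | more than 5 mm |
| Grade | Gleason pattern 4 or higher | none |
| PSMA staining | none | positive |
| Dominance | none | required, undefined |

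The sets overlap: any lesion of 0.5 cm³ or more also exceeds 5 mm. They still differ both ways. A 7 mm, PSMA-positive, dominant lesion with pattern 3 only can count in the endpoint but is outside the objective. A PSMA-negative or non-dominant lesion of 0.5 cm³ or more with pattern 4 is in the objective but not in the endpoint.

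**4. Does another stated analysis give the objective's detection proportion?**
- Section 9.1.2.1 contains the objective's lesions but does not separate them by grade.
- The GEE analysis in Section 12.1 estimates PPV and NPV, which are not detection proportions. Its subgroups do not help: "Subgroup analyses will be performed for high, moderate, and low risk disease (see secondary endpoints"), and no such classes are defined there.
- The ROC analysis relates SUV to any disease and to a severity that is not defined.
- The sector-based sensitivity has no size or grade condition.
- The first secondary analysis tests identified against unidentified lesions on size, PSMA staining and Gleason score, each separately.
- The proportion of positivity by size and grade listed in Section 1.2 becomes Spearman correlations of SUV in Section 12.1. The one grade grouping compares SUVmax "measurements between lesions with low Gleason score (3+4 or lower) and high Gleason score (4+3 or higher"). It puts 3+4 in the low group, although such a lesion contains pattern 4.
- The analysis that does use the clinical-significance criteria covers lesions that fail them.

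None gives the proportion, per patient or per lesion.

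**5. The complement.** Sections 1.2 and 12.1 define lesions that are not clinically significant as below 0.5 cm³ with pattern below 4. Lesions of 0.5 cm³ or more with pattern 3 only, and smaller lesions with pattern 4, fall in neither class.

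**6. Precision if the denominator is only patients with a qualifying lesion.** Eligibility (Section 3.1) sets no lesion size, grade or PSMA criterion, so fewer than 20 might qualify. For assumed counts at p = 0.75:
- n = 16: 1.96 × √(0.1875/16) = 21.2 points.
- n = 12: 1.96 × √(0.1875/12) = 24.5 points.

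**The case against.** **The objective names no per-patient measure.** This stands. A lesion-level proportion could answer it, and Section 9.1.2.1 lacks only the grade restriction. The gap is that neither a per-patient nor a per-lesion proportion is stated for these lesions.

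**The method line for non-significant lesions implies a counterpart for significant ones.** It does hint at one. But the analyses above it are not restricted to significant lesions, and no detection proportion for them is written down.

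**Section 12 refers to published studies for its analysis strategy.** They could contain more detail, so the claim is limited to what these documents state.

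**This is a pilot, and size and Gleason score are recorded for every focus (Section 9.1.4.1).** Little information would be lost for good. That limits the harm. Pilot status explains the missing power calculation, but not a main result that answers another question.

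**A reader might infer that the endpoint flatters the tracer, because PSMA-negative lesions drop out instead of counting as misses.** The documents do not support this. It assumes that the denominator is only patients with a qualifying lesion. Sections 12.1 and 12.2 compute precision for all 20 patients, and on that reading a patient without such a lesion is a non-success. The PSMA background in Section 2.1 also says nearly all prostate cancers express PSMA, so such lesions may be few. Admitting smaller and lower-grade lesions could move the proportion the other way.

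**A reader might also infer that ±19.0 points is wrong.** It is correct for its inputs. Only its denominator is unclear.

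**Conclusion.** The mismatch is real on the text. The primary objective and primary endpoint differ on size, grade, PSMA status and dominance, and no stated analysis isolates the objective's lesions. The headline proportion and the interim determination therefore do not measure the stated objective.

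The 7.6-fold gap between the volume thresholds assumes spherical lesions. The effect on the reported proportion cannot be estimated in size or direction. Section 12.3 states no decision rule, so the consequence for the interim determination cannot be quantified either. This should be fixed. The two definitions must be reconciled, but the documents do not require the existing endpoint to be discarded.

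**What to change.** Use one lesion definition in Sections 1.1 and 12.1, by either route:

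- **(a) Add the objective's proportion to Section 12.1**, as primary or reported beside the existing endpoint. Among patients with at least one lesion of 0.5 cm³ or more and Gleason pattern 4 or higher at prostatectomy, whatever the PSMA staining, give the proportion whose such lesion is identified on 89Zr-df-IAB2M PET. State an index-lesion rule for multifocal disease, the denominator and a 95% interval. Report the same lesions as a subset of the analysis in Section 9.1.2.1.
- **(b) Reword Section 1.1 to match the endpoint**, and do not describe the result as detection of clinically significant cancer.

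With either route:
- Define dominance.
- State whether 3+4 counts as pattern 4 or higher.
- Define lesions that are not clinically significant as all those that do not meet both criteria.
- State whether the denominator is all 20 patients or only those with a qualifying lesion. If the latter, say that ±19.0 points applies only when all 20 qualify, and give half-widths for smaller counts.

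The cost is protocol and SAP text plus a volume classification for each focus. Section 9.1.2.1 already needs that classification, although Section 9.1.4.1 lists size without saying how volume is derived. Route (a) may give a smaller denominator and a wider interval.

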#### **a) Diagnostic value of Ga-PSMA-HBED-CC PET/CT imaging in the diagnosis of recurrent prostate cancer:**

The study reports data from a retrospective analysis of 319 patients who underwent Ga-PSMA-ligand PET/CT from 2011 to 2014. The Ga-PSMA-HBED-CC solution was applied to the respective patient via an intravenous bolus injection (mean of 172.4 MBq ±70.9, range 40 – 400 MBq, median 161 MBq). A non-contrast-enhanced CT scan was performed 1-hour post tracer injection. Histological verification was performed in 42 patients after the Ga-PSMA-ligand PET/CT. Tracer uptake was measured in 901 representative tumor lesions. 82.8% of the patients had at least one lesion indicative of PCa was detected. Tumor-detection was positively associated with PSA level and Androgen deprivation therapy (ADT). Gelason Score and PSA doubling time (PSA-DT) were not associated with tumor-detection. The average maximum standardized uptake value (SUVmax) of tumor lesions was 13.3 ± 14.6 (0.7-122.5). Amongst lesions investigated by histology, 30 were false-negative in 4 different patients, and all other lesions (n = 416) were true-positive or true-negative. A lesion-based analysis of sensitivity, specificity, negative predictive value (NPV) and positive predictive value (PPV) revealed values of 76.6%, 100%, 91.4% and 100%. A patient-based analysis revealed a sensitivity of 88.1%.

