#### **b) PET imaging with a Ga-PSMA ligand for the diagnosis of prostate cancer: biodistribution in humans and first evaluation of tumor lesions :**

Initial clinical studies with the Ga-labeled *PSMA-HBED-CC* were conducted at Heidelberg University Hospital and the German Cancer Research Center to assess

the biodistribution of  $^{68}\text{Ga}$ -PSMA-HBED-CC in normal tissues and tumor lesions. A total of 37 patients with prostate cancer and rising PSA levels were subjected to  $^{68}\text{Ga}$ -PSMA-HBED-CC PET/CT imaging. Quantitative assessment of tracer uptake was performed 1 and 3 h post-injection by analysis of mean and maximum standardized uptake values (SUVmean/max) of several organs and 65 tumor lesions. Subsequently, tumor to background ratios were calculated.

The  $^{68}\text{Ga}$ -PSMA-HBED-CC PET/CT images showed intense tracer uptake in both kidneys and salivary glands. Moderate uptake was seen in lacrimal glands, liver, spleen and in small and large bowel. Quantitative assessment revealed excellent contrast between tumor lesions and most normal tissues. Of 37 patients, 31 (83.8 %) showed at least one lesion suspicious for cancer at a detection rate of 60 % at PSA <2.2 ng/ml and 100 % at PSA >2.2 ng/ml. Median tumor to background ratios were 18.8 (2.4-158.3) in early images and 28.3 (2.9-224.0) in late images. Within healthy organs, kidneys and salivary glands demonstrated the highest radiotracer uptake. Lesions suspicious for prostate cancer presented with excellent contrast as early as 1-hour after injection with high detection rates even at low PSA levels.

**c)  $^{68}\text{Ga}$ -labeled PSMA ligand as superior PET tracer for the diagnosis of prostate cancer: Comparison with  $^{18}\text{F}$ -FECH :**

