  - The Spearman-rank correlation coefficient will be used to evaluate the association between SUV and serum PSA levels obtained during screening.
- To determine the ability of *in vivo*  $^{89}\text{Zr}$ -df-IAB2M PET/CT to identify extra-prostatic extension:
  - The Wilcoxon rank-sum test will be used to compare  $\text{SUV}_{\text{max}}$  measurements of IAB2M-positive extra-prostatic sites between lesions with and without histopathologically confirmed extra-prostatic extension.
- To determine the ability of *in vivo*  $^{89}\text{Zr}$ -df-IAB2M PET/CT to identify occult lymph node involvement:

- The Wilcoxon rank-sum test will be used to compare  $SUV_{max}$  measurements of IAb2M-positive lymph nodes between patients with and without histopathologically confirmed lymph node involvement.
- To further evaluate the safety of  $^{89}Zr$ -DF-IAB2M PET/CT and  $^{68}Ga$ -PSMA-HBED-CC imaging.
  - See section on Risks

Additionally, we will assess whether there is improved sensitivity in detecting localized PCa by combining imaging results. This assessment will be done by estimating the PPV with different combinations of imaging modalities. The incremental effect of an additional imaging modality on PPV will be tested with the Wald test, as described by Turkbey B, et al.

All p-values will be two-sided with statistical significance evaluated at the 0.05 alpha level. All analyses will be performed in SAS Version 9.4 (SAS Institute, Inc., Cary, NC) and Stata Version 13.0 (StataCorp, College Station, TX).

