## 12.2 Sample Size/Accrual Rate

The sample size for this study will be 20 patients. We anticipate an accrual rate of at least two patients per month. With a sample size of 20 patients in the study, a two-sided 95% confidence interval for the proportion of patients successfully imaged by  $^{89}Zr$ -df-IAB2M can be constructed to be within  $\pm 19.0\%$  of the observed proportion of patients with successful imaging by  $^{89}Zr$ -df-IAB2M. This calculation assumes an  $^{89}Zr$ -df-IAB2M imaging-success proportion of 75%. All estimates from the study will serve as preliminary data (i.e., hypothesis-generating) for future studies.”

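### With only a random intercept, the tumour v non-tumour SUVmax model understates its standard error if the contrast varies between patients who contribute several regions

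*Combined protocol and SAP*

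**What the plan says.** Section 12.1, under the primary endpoints and the lesion-based analysis, states that SUVmax measurements "obtained in tumor and non-tumor regions will be compared". The method is given as "a linear mixed-effects model with a random intercept will be used to estimate and compare the mean" SUVmax values by region, and its stated purpose is "To account for inpatient correlation of multiple lesions" (evidently within-patient correlation). A threshold of P < 0.05 is attached to this comparison, and the end of the secondary-endpoint text adds that "All p-values will be two-sided with statistical significance evaluated at the 0.05 alpha level". Section 12.2 fixes the number of clusters: "The sample size for this study will be 20 patients".

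The random intercept is the only random effect named. No robust variance and no small-sample degrees-of-freedom method is named for this model. The number of tumour and non-tumour regions per patient is not stated, nor is any variance for SUVmax with the study tracer.

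Other analyses are better protected. The next bullet in 12.1 uses robust variance for the predictive values, and the sector-based comparison with mpMRI reduces the data to one sensitivity and one specificity per patient before testing.

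**The concern.** Tumour v non-tumour is largely a within-patient factor. The random intercept captures how high or low a patient's uptake is overall, and that part cancels from the contrast. What the contrast needs, and the model lacks, is a term for how much the tumour-minus-non-tumour difference itself varies from patient to patient. Without it, the regions of one patient count as independent information on that difference.

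Several regions per patient are to be expected. The plan speaks of multiple lesions, the PET reader records every suspicious area (9.1.2.1), and the pathologist outlines every tumour focus (9.1.4.1). A constant contrast is implausible: section 2.2 and its neighbouring background text on PSMA describe expression rising with grade, and the plan intends subgroups by risk.

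At stake are the reported p-value and, more usefully, the confidence interval for the tumour/non-tumour contrast, which would be carried forward as preliminary data for later studies.

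**Working it through.** **The plan's own figure.** The only precision statement is for the imaging-success proportion: 1.96 × √(0.75 × 0.25 / 20) = 0.190, so ±19.0% reproduces. It does not concern the SUVmax model, for which the plan gives no figure.

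**Inputs.** From the documents: N = 20 patients (12.2) and a two-sided test at 0.05 (12.1). Assumed, because the documents do not give them: mT tumour and mN non-tumour regions in each patient, residual SD σ, and SD τ of the patient-specific difference. Type I error depends on τ/σ only.

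**Formulas.** Let m = mT + mN and h = mT·mN/m, so that 1/mT + 1/mN = 1/h.

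- True variance of the estimated contrast: (τ² + σ²/h)/N.
- Variance reported by the random-intercept model: s²/(hN), with s² = [N(m−2)σ² + (N−1)(σ² + hτ²)] / [N(m−1) − 1]. Part of the contrast variation leaks into s², but not enough.
- Type I error with a normal reference: 2[1 − Φ(1.96 × model SE / true SE)].

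**2 tumour + 4 non-tumour regions, τ = σ = 1.** h = 8/6 = 1.333. s² = (80 + 19 × 2.333)/99 = 1.256. Model variance = 1.256 × 0.75/20 = 0.0471, SE 0.217. True variance = (1 + 0.75)/20 = 0.0875, SE 0.296. The ratio is 0.734, so the SE is 27% too small. Type I error is about 15% and coverage of the 95% interval about 85%. With σ = τ = 0.4 the same SEs read 0.087 and 0.118.

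**1 + 2 regions, τ = σ = 1.** h = 0.667. s² = (20 + 19 × 1.667)/39 = 1.325. Model variance = 1.325 × 1.5/20 = 0.0994, SE 0.315. True variance = 2.5/20 = 0.125, SE 0.354. Ratio 0.892, type I error about 8%.

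**Range.** Type I error (%) at nominal 5%:

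| Regions (tumour + non-tumour) | τ/σ = 0 | 0.5 | 1 | 1.5 |
|---|---|---|---|---|
| 1 + 1 | 5.0 | 5.0 | 5.0 | 5.0 |
| 1 + 2 | 5.0 | 5.9 | 8.1 | 10.3 |
| 2 + 2 | 5.0 | 6.8 | 11.1 | 15.3 |
| 2 + 4 | 5.0 | 8.0 | 15.0 | 21.9 |
| 3 + 3 | 5.0 | 8.4 | 15.9 | 22.9 |
| 2 + 6 | 5.0 | 8.7 | 17.4 | 25.7 |
| 3 + 9 | 5.0 | 10.8 | 23.5 | 34.0 |

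**Simulation check** (REML fits, Wald test, 1,000 runs per setting, Monte Carlo SE about 0.7 points), for τ/σ = 0 / 0.5 / 1 / 1.5:

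- 1–4 tumour and 1–4 non-tumour regions: 4.8 / 8.0 / 16.2 / 22.7%.
- 1–4 tumour and 6 non-tumour regions: 4.9 / 8.2 / 21.0 / 29.5%.
- 1 + 1 regions: 7.0–7.5% at every τ. This excess does not grow with τ and is consistent with a normal rather than a t reference at N = 20.

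A paired t-test on patient-level mean differences gave 4.5–6.1% in every setting. A model with a by-patient random region effect was run in two settings (1–4 and 1–4 regions, 600 runs each): 3.7% at τ = 0 and 4.8% at τ/σ = 0.5, with frequent convergence warnings.

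**The case against.** The strongest reply is that the problem is conditional and the documents do not supply the conditions. With one region of each kind the model amounts to a paired analysis, and with a constant contrast there is nothing to miss. That stands, and it is why the size is given as a range.

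A reader might take the background section as proof of the missing variance: "Median tumor to background ratios were 18.8 (2.4-158.3) in early images" and a mean SUVmax that "of tumor lesions was 13.3 ± 14.6 (0.7-122.5"). It is not. Both come from the 68Ga tracer, in patients with rising PSA or recurrent disease, and pool lesions, so between-lesion and between-patient spread cannot be separated. They do not estimate τ, nor do they show how residuals would be distributed for the study tracer in localized disease.

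A reader might also infer that the model ignores patient variation in uptake, or that its SE depends on regions instead of patients. Neither is right. Shared uptake is in the intercept, and N stays in the denominator. With σ = τ = 0.4, going from 2 + 4 to 2 + 10 regions moves the model SE only from 0.087 to 0.074, while the true SE moves from 0.118 to 0.113.

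Finally, a zero contrast may be remote. If the ratio were as low as 2.4 (log 0.875), z would be about 7.4 with the true SE of 0.118 and about 10 with the model SE of 0.087, and the test conclusion would be the same. This weakens the type I error argument but not the one about the interval, whose coverage is low wherever the true contrast lies.

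**Conclusion.** The point holds in conditional form. As written, the model gives too small a standard error whenever the tumour-minus-non-tumour difference varies between patients and patients contribute more than one region of a kind. The second condition is expected by the plan; the first is likely, since grade and PSMA expression differ, but is not quantified anywhere in the documents. Type I error runs from 5% (no inflation), through about 8% (1 + 2 regions) and 15% (2 + 4) when the contrast SD equals the residual SD, to about 34% (3 + 9 regions, contrast SD 1.5 times the residual SD). All region counts and SDs are assumptions.

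Because the model sits under the primary-endpoint heading, a reader might infer that the trial's main result is affected. The documents do not support that. The primary endpoint is a patient-level proportion, the interim look in 12.3 is based on it, and all estimates are declared hypothesis-generating. The consequence is an overconfident secondary estimate, not a flawed trial conclusion.

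**What to change.** In 12.1, base inference for this comparison on the patient:

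- Either add a by-patient random effect for region type (tumour v non-tumour) with small-sample degrees of freedom, or keep the model and use cluster-robust standard errors with a small-sample correction.
- Name a fallback, since the richer model may not converge with 20 patients: average SUVmax per patient within tumour and within non-tumour regions, and make a paired comparison on n − 1 degrees of freedom (19 if all 20 patients contribute both).
- State how many tumour and non-tumour regions are measured per patient, and report the difference with its 95% confidence interval.

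Analysing log SUVmax is optional and belongs in a sensitivity analysis, because it replaces the planned difference in mean SUVmax with a ratio.

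The cost is a few sentences of plan text and a few lines of code, with no change to sample size or conduct. The downside is a wider interval: at 2 + 4 regions with equal SDs, about 1/0.734 = 1.36 times as wide.
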